3.4. Baseline Variables

The following baseline variable will be included as a factor:

Baseline fibrosis stage (F2/F3)

For all biopsy based efficacy endpoints, baseline will be defined as the biopsy results obtained at SCR2 or a historical biopsy within 12-weeks prior to SCR2 (though within 24-weeks of Day 1 (Visit 5).

For Liver Fat as measured by MRI-PDFF, baseline is defined as the value of total mean liver fat obtained between Visit 4 and Visit 5 (ie, labeled as baseline).

For Liver Volume as measured by MRI-PDFF, baseline is defined as the value of total mean liver volume obtained between Visit 4 and Visit 5 (ie, labeled as baseline).

Baseline for FibroScan® based endpoints will also be defined as the evaluable values obtained between Visit 4 and Visit 5 or SCR1 if there isn't an evaluable value between Visit 4 and Visit 5 (ie, labeled as baseline).

For all Patient Reported Outcomes, any other continuous efficacy endpoints and all safetyrelated continuous endpoints, baseline will be defined as the closest results obtained prior to dosing on Day 1 (Visit 5)

For laboratory results, the baseline value to be used will be either Day 1 or Day -14 (plus any allowable analysis windows – see Appendix 2.1), but not any further back than this. If laboratory collections have been taken in the correct fasted state (as indicated in the CRF), Day 1 should be used, but if not, then Day -14 should be used (again, if in the correct fasted state for the specific laboratory parameter).

For vital signs, the baseline value to be used will be either Day 1 or Day -14, but not any further back than this. If possible, Day 1 should be used, but if this is missing, then Day -14 should be used. If both Day -14 and Day 1 is missing for a particular parameter, then the baseline should be considered as "Missing".

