- Completed by participants, at home (or on-site) on sponsor-provided ePRO device at set frequency (eg, once-a-day on selected days or over 14-day interval) as prompted by device/site (see Table 4)

SoA-Table A2: Blood and Urine Collections in Study C2541013

Visit Identifier	PreQ	SCR1	SCR2	Run-In	Baseli	[All (ctions appli			ornir	ıg do	se of		y inte					when	Follo	ř	IP D/C or Study D/Ce
Weeks ^a Relative to Dosing on Day 1				-6	-2	0	2	4	6	8	12	16	20	24	28	32	36	40	44	48	50	52b)/C
Visit #	0	1	2	3	4	5	6	7	8	9	10	11	12	13	14	15	16	17	18	19	20	21	IP I
On-site (x) [with Telephone (T)b] visits	x	X	х	x or T	x	X	X	X	x	x	X	X	T	X	T	x	T	X	T	x	X	T	x
Blood collection (following overnight fast of≥8-hou	rs)	for –	Г																				
FSH (females only), serology (HBsAg, HCVAb, HIV), a1-antitrypsin, ceruloplasmin	Хď	X ^d]																				
%CDT	X ^d	X ^d			X ^d	X														X			x
Hematology, chemistry, coagulation	Хď	X ^d	1		X ^d	X	X	X	X	x	X	X		х		х		X		X	X	X°	x
Pregnancy (females only)	Хď	Хď	1		X ^d	X	X	х	X	х	X	X		х		х		X		х	X	X°	x
Triglycerides, direct LDL-C, HDL-C, total cholesterol	Хď	X ^d	s	su	X ^d	x	x	x	x	x	X	X	su	x	su	х	su	x	su	X	X	X°	x
HbA1C, Plasma Glucose	$\mathbf{x}^{\mathbf{d}}$	Хď	ctio	ectio	X ^d	х		х		х		х	ectio	х	ectio	х	ectio	х	Collections	х	Х		П
Direct VLDL, ApoA1, ApoBtotal, ApoB100, ApoB48, ApoC3, ApoE	Г		o Blood or Urine Collections	io Blood or Urine Collections	x	X		x		х		X	Urine Collections	X	o Blood or Urine Collections	x	Urine Collections	x	e Colle	X	X		
PCSK9, plasma insulin, adiponectin, CK18-M30, CK18-M65, ProC3, ProC6, ELF test, hs-CRP			or Uri	or Uri	x	x		X		X		X	or Urii	x	or Urii	x	or Urii	x	or Urine	X	X		
Predose PK - DGAT2i and ACCif	Γ		poo	pool		х	X			X	X	X	o Blood		pool	x	o Blood or		lo Blood	X			
Post dose PK - DGAT2i and ACCi ^{f,g}	Г		No B	No B			Χg			Χ ^g	Χ ^g	Χg	lo B		lo B		lo B		lo B				\Box
CCI																							
Spot urine collection for –																							
Urine drug test	Хď	X ^d]		X ^d																		
Urinalysis (and microscopy when appropriate)	Хď	X ^d	1		x	х	x	x	x	х	х	х		х		х		x		x	х	X°	x
On-site pregnancy test (WOCBP only)	Г		1		X ^h	x ^h	x ^h	x ^h	X ^h	X ^h	x ^h	X ^h		X ^h		X ^h		X ^h		x	X	X°	x

SoA-Table A2: Blood and Urine Collections in Study C2541013

Visit Identifier	PreQ	SCR1	SCR2	Run-In	Baseline	[All		ctions appli			ornii	ıg do		study	inte					when		dn-	or Study D/Cc

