To assess the safety and tolerability with a range of DGAT2i doses administered alone, and coadministration of DGAT2i + ACCi, compared to placebo, and the coadministration of DGAT2i + ACCi relative to DGAT2i alone		Assessment of TEAEs, safety- related clinical laboratory tests, vital signs, and 12-lead ECGs, over time up to Week 48
Tertiary/Exploratory:		
To evaluate the effect of a range of DGAT2i doses administered alone, and coadministration of DGAT2i + ACCi, compared to placebo, and the coadministration of DGAT2i + ACCi relative to DGAT2i alone, in participants with worsening of biopsy endpoint components		Proportion of participants with worsening in liver biopsy endpoint components based on assessment by sponsor-identified central pathologist(s) at Week 48 – • Progression of fibrosis by ≥1 stage • Worsening of ≥2 points in Total NAS

For all endpoints, baseline is defined as the evaluable result closest prior to dosing on Day 1/Visit 5

Additional tertiary/exploratory objectives and endpoints are listed in Section 9.4.7.

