Descriptive summaries of the observed values and percent change from baseline for each treatment group will also be produced.

Treatment effects over time

A Mixed-effects model with repeated measures (MMRM) will be used for the analysis of continuous endpoints with more than one post-baseline collection time point. All observed data collected during the post-baseline treatment period will be utilized, including follow-up data in order to assess the impact of stopping treatment on the endpoint MMRM analysis will be performed with treatment, study week (nominal timepoint) and treatment-by-study week interaction as fixed effects, and baseline value of the analysis endpoint as a covariate, baseline (SCR2 Eligibility) fibrosis stage (F2/F3) as a factor. If the endpoint being analyzed is log-transformed, the baseline value of the analysis endpoint will also be log-transformed. Repeated measures model with unstructured covariance matrix will be utilized. If this does not converge then compound symmetry structure will be considered. Additionally, the number of covariates may be reduced to improve model fit. Estimates of treatment effects will be assessed using Least Square Means (LSMs) and CIs at each time point. LSM difference for each comparison along with the corresponding 90% CI will be provided. For log-transformed endpoints, the mean relative changes (RC) and their CIs will be exponentiated and percent change will then be determined as follows: Percent change = 100* (RC − 1). If there are major deviations from the statistical assumptions underlying this model then alternative transformations (eg, log) or non-parametric analyses may be presented.

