Appendix 2. Data Derivation Details

Appendix 2.1. Definition and Use of Visit Windows in Reporting

Each collected assessment will be mapped to its actual visit window according the following algorithm described in the table below:

Visit label	Protocol defined Window (days)	Visit	Visit window as part of final reporting*
			For efficacy, PD, PK and safety endpoints
Pre-Qualification	N/A	1	N/A
Screen 1	N/A	2	N/A
Screen 2	N/A	3	N/A
Run-In	N/A	3	N/A
Week -2	-14 ± 4	4	Between Week 0 and Week -2, data are used to define baseline
Week 0	1	5	Baseline will be result closest prior to dosing on randomized regimen on Day 1 [Visit 5] Window for baseline measurements is from Day -22 to Day 1 [Visit 5] pre-dose (The only exception is for Height, for which any measurement from PreQ to Day 1 pre-dose can be used, and for Fibroscan® for which the last evaluable measurement from SCR1 to Day 1 pre-dose can be used) Label as 'BASELINE'
Week 2	14 ± 4	6	
			'Date of assessment' – 'Baseline date' + 1 = [8, 21]; ie, - 6 days to +7 days
Week 4	28 ± 4	7	'Date of assessment' – 'Baseline date' + 1 = [22, 35]; ie, -6 days to +7 days
Week 6	42 ± 4	8	'Date of assessment' – 'Baseline date' + 1 = [36, 49]; ie, -6 days to +7 days
Week 8	56 ± 4	9	'Date of assessment' – 'Baseline date' + 1 = [50, 70]; ie, -6 days to +14 days
Week 12	84 ± 4	10	'Date of assessment' – 'Baseline date' + 1 = [71, 98]; ie, -13 days to +14 days
Week 16	112 ± 4	11	'Date of assessment' – 'Baseline date' + 1 = [99, 140]; ie, -13 days to +28 days
Week 24	168 ± 4	13	'Date of assessment' – 'Baseline date' + 1 = [141, 196]; ie, -27 days to +28 days
Week 32	224 ± 4	15	'Date of assessment' – 'Baseline date' + 1 = [197, 252]; ie, -27 days to +28 days
Week 36**	252 ± 4	16	'Date of assessment' – 'Baseline date' + 1 = [197, 308]; ie, -55 days to +56 days
Week 40	280 ± 4	17	'Date of assessment' – 'Baseline date' + 1 = [253, 308]; ie, -27 days to +28 days
Week 48	336 ± 4	19	'Date of assessment' – 'Baseline date' + 1 = [309, 343]; ie, -27 days to +7 days
Week 50 (1st		20	'Date of assessment' – 'Date of last dose' + 1 = [7, 27];
Follow-up visit)			ie, any time after 7 days and up to 28 days after last dose.
Week 52 (2nd	≥28- and ≤35- days		'Date of assessment' – 'Date of last dose + 1 ≥ 28;
Follow-up visit)	post last dose at	1	ie, any time after 28 days after last dose

Visit label	Protocol defined Window (days)	Visit	Visit window as part of final reporting*
			For efficacy, PD, PK and safety endpoints

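### Most blood biomarkers are drawn twice before randomised dosing but the MMRM adjusts for one value; adding the Visit 4 value is an optional, low-priority gain in precision

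*SAP*

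**What the plan says.** SoA-Table A2 (Protocol 1.3) schedules several groups of analytes at both Visit 4/Baseline (Week -2) and Visit 5/Day 1:

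- "PCSK9, plasma insulin, adiponectin, CK18-M30, CK18-M65, ProC3, ProC6, ELF test, hs-CRP"
- "Direct VLDL, ApoA1, ApoBtotal, ApoB100, ApoB48, ApoC3, ApoE"
- "Triglycerides, direct LDL-C, HDL-C, total cholesterol"
- the chemistry and hematology row, and the HbA1C and plasma glucose row.

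Both draws precede randomised dosing. Protocol 4.2 describes the interval between them as a fixed two-week single-blind placebo period. Protocol Appendix 2 removes ProC3, ProC6 and direct VLDL for participants in one country.

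Protocol section 3 sets one rule for all endpoints: "baseline is defined as the evaluable result closest prior to dosing on Day 1/Visit 5". SAP 3.4 applies it to laboratory values: "For laboratory results, the baseline value to be used will be either Day 1 or Day -14". If Day 1 was collected in the correct fasted state, "Day 1 should be used, but if not, then Day -14 should be used". SAP Appendix 2.1 also takes the single closest pre-dose result.

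The MMRM in SAP 5.2.2 has treatment, week and their interaction, baseline fibrosis stage, and "baseline value of the analysis endpoint as a covariate". SAP 6.3.6.1 repeats this for the continuous exploratory endpoints. Neither document uses both pre-dose values in a model.

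**The concern.** One laboratory value carries assay error and day-to-day variation. A second value of the same analyte, taken about two weeks earlier and also before randomisation, can absorb some of that noise when used as a covariate. Because it is measured before randomisation, adjusting for it does not bias the treatment contrast.

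The contrasts concerned are the trial's randomised evidence on mechanism, lipids, liver tests and non-invasive response, with about 50 randomised per arm. SAP 6.3.6.1 reports them with 90% intervals, and with 50% intervals for combination against monotherapy. The samples are already scheduled, so any precision they offer needs no further visit or blood draw.

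**Working it through.** **No figure to reproduce.** The documents state no variance, correlation or precision for any blood biomarker. The sample size in Protocol 9.2 rests on the biopsy endpoint.

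**Inputs from the documents.** Two scheduled pre-dose draws about two weeks apart; one baseline covariate in the model; 50 randomised per arm and about 40 evaluable (Protocol 4.1, the latter for the biopsy endpoint).

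**Inputs assumed.** r1 = correlation of Day 1 with follow-up; r2 = correlation of Visit 4 with follow-up; rb = correlation of Visit 4 with Day 1. All are on the analysis scale.

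**Formula.** With Day 1 as the only covariate, residual variance is 1 − r1². Adding Visit 4 as a separate covariate lowers this by the fraction

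g = (r2 − r1·rb)² / [(1 − r1²)(1 − rb²)]

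and interval width is multiplied by √(1 − g). Once Day 1 is a covariate, modelling log change from Day 1 or the log follow-up value gives the same contrast. The formula is for one follow-up time. The MMRM uses one baseline coefficient across visits, so it is an approximation there.

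**Example.** rb = 0.8, r1 = 0.6, r2 = 0.58: (0.58 − 0.48)² / (0.64 × 0.36) = 0.0100 / 0.2304 = 4.3%.

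| Assumption | rb | r1 | r2 | Variance reduction | Interval narrower by |
|---|---|---|---|---|---|
| Visit 4 slightly less predictive than Day 1 | 0.8 | 0.6 | 0.58 | 4.3% | 2.2% |
| | 0.7 | 0.5 | 0.48 | 4.4% | 2.2% |
| | 0.7 | 0.6 | 0.57 | 6.9% | 3.5% |
| | 0.8 | 0.7 | 0.68 | 7.8% | 4.0% |
| Visit 4 less predictive by 0.05 | 0.85 | 0.5 | 0.45 | 0.3% | 0.2% |
| | 0.9 | 0.7 | 0.65 | 0.4% | 0.2% |
| | 0.8 | 0.6 | 0.55 | 2.1% | 1.1% |
| | 0.7 | 0.5 | 0.45 | 2.6% | 1.3% |
| Visit 4 less predictive by 0.10 | 0.85 | 0.6 | 0.5 | 0.1% | under 0.1% |
| Visit 4 as predictive as Day 1 | 0.8 | 0.5 | 0.5 | 3.7% | 1.9% |
| | 0.8 | 0.6 | 0.6 | 6.2% | 3.2% |
| | 0.8 | 0.7 | 0.7 | 10.7% | 5.5% |
| All three correlations equal | 0.5 | 0.5 | 0.5 | 11.1% | 5.7% |
| | 0.6 | 0.6 | 0.6 | 14.1% | 7.3% |
| | 0.7 | 0.7 | 0.7 | 17.0% | 8.9% |
| | 0.8 | 0.8 | 0.8 | 19.8% | 10.4% |

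**Simulation check.** A two-arm ANCOVA with 40 per arm and 8,000 runs per case, entering both values as separate covariates, gave 10.3% (r1 = r2 = rb = 0.5), 5.1% (r1 = r2 = 0.6, rb = 0.8) and 15.4% (all 0.7). The formula gives 11.1%, 6.2% and 17.0%. The shortfall is about the price of one extra term in 80 participants (1/80 = 1.25%).

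**Price of the extra terms in the full model.** Roughly 1/280 = 0.36% of variance per term, so about 0.7% for the covariate plus a missing indicator. Where g is near zero, the net effect is neutral to very slightly negative.

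**Why not average the two draws.** The mean of the two leaves variance 1 − (r1 + r2)² / [2(1 + rb)]. With r1 = 0.60, r2 = 0.50, rb = 0.85 this is 1 − 1.21/3.70 = 0.673, against 0.640 for Day 1 alone, a loss of 5.2%. Averaging would also require a change to the protocol's baseline definition. A second covariate avoids both problems, because its weight is estimated from the data.

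**The case against.** The strongest reply is that nothing here is wrong. The single closest pre-dose value is the protocol's rule, the SAP follows it and gives a fasting fallback, and adjusting for one baseline is valid. No hypothesis tests are planned (Protocol 9.1.2, SAP 5.1), and no stated decision turns on a slightly narrower biomarker interval. All of that stands, and it is why the point is optional.

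A reader might infer from the equal-correlation rows that the plan forgoes 11 to 20% of variance on every contrast, equivalent to 12.5 to 24.6% more participants (1/0.889 and 1/0.802, before rounding). The documents do not support that reading. They give no correlations, and those rows require two draws two weeks apart, both off active drug, to agree no better with each other than Day 1 agrees with Week 48 after treatment.

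Timing also limits the gain for some analytes. The note to Protocol Figure 1 runs the stabilization period from Run-In to Day 1, so Visit 4 falls inside it. Metformin above 1 g/day is reduced at Run-In (Protocol 6.5.1), and certain lipid agents are switched then (Protocol 6.5.2). Glycemic and lipid values may still be drifting at Visit 4. An estimated coefficient gives such a value less weight, so the consequence is a smaller gain, not bias.

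Finally, a bare second covariate would be incomplete. Where Day -14 has replaced a non-fasted Day 1, it would enter the same number twice, and a non-fasted Visit 4 value must be set to missing for fasted analytes (SAP 3.5.2 and 5.3). Both cases need a rule.

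**Conclusion.** The point holds as a modest improvement in efficiency. Most blood biomarkers have two values before randomised dosing and the MMRM uses one. Using the second should lower residual variance by roughly 0 to 8%, with intervals at most about 4% narrower. At the upper end, 40 participants per arm would act like about 43 (40/0.922). The direction follows from the design; the size rests wholly on assumed correlations. Gains above that range need Visit 4 to predict follow-up as well as Day 1 does, and the two draws to correlate little or no better with each other than with follow-up. For analytes still drifting after Run-In changes, expect the low end.

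A reader might also infer that the SAP's baseline rule is defective or that the main results are at risk. Neither follows. The rule is consistent and unbiased, and the biopsy and MRI-PDFF analyses do not use these values. This is a low-priority, optional change to tertiary/exploratory analyses.

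**What to change.** Before unblinding, amend SAP 5.2.2 and 6.3.6.1 for the blood biomarkers:

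1. Keep Day 1 as the reference for change or percent change, with the SAP 3.4 fallback unchanged.
2. Add the Visit 4 value of the same analyte as a second covariate, log-transformed where the endpoint is.
3. Treat that covariate as missing when Visit 4 is absent, when it was not correctly fasted for a fasted analyte, or when Day -14 has already replaced Day 1 as the baseline. Fill in the overall mean across arms and add a missing indicator.
4. Name it as a term to drop if the model does not converge, under the SAP's existing allowance to reduce covariates. This matters most in the smaller T2DM subset.

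The cost is one or two model terms per analyte and a fill-in rule. No sample, visit or protocol amendment is needed, because the baseline definition does not change.

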3.5. Safety Endpoints

3.5.1. Adverse Events

An adverse event will be considered treatment emergent relative to a given treatment if:

 The event starts on or after the first dosing day of double-blinded study medication on Day 1 [Visit 5], but before the last dose plus the lag time. The algorithm will not consider any events that started prior to the first dose date. If an AE starts on the same day as the first dose date, it will be considered treatment emergent. Any AEs that occur after signing Informed Consent and before randomization and the first dose of double-blind study medication should be recorded in Medical History; with only treatment emergent AEs reported on the AE CRF page.

The effective duration of treatment is determined by the lag time defined as the Pfizer Standard of 999 days post last dose of double-blinded study medication (i.e. an infinite lag). Any treatment-emergent event occurring within the lag time, whether it occurs during a break in treatment or at the end of treatment, will be attributed to the assigned randomized regimen.

A 3-tier approach will be used to summarize AEs. Under this approach, AEs are classified into 1 of 3 tiers. Different analyses will be performed for different tiers (see Section 6.6.1).

Tier 1 events: These are prespecified events of clinical importance and are maintained in a list in the product's Safety Review Plan.

Tier 2 events: These are events that are not tier 1 but are "common." A Medical Dictionary for Regulatory Activities (MedDRA) preferred term (PT) is defined as a Tier 2 event if there are at least 4 participants with at least one occurrence in any treatment group.

Tier 3 events: These are events that are neither Tier 1 nor Tier 2 events.

3.5.2. Laboratory Data

For the specific laboratory parameters listed in Table 3 below, the following endpoints will be evaluated using CDISC and Pfizer standards (CaPS):

- Absolute value and change from baseline at each visit (Week 2, 4, 6, 8, 12, 16, 24, 32, 40, 48 and Follow-up).
- Number of occurrences of these abnormalities defined as "Flag Level" or "Alert Level"
- Number of participants with these abnormalities defined as "Flag Level" or "Alert Level"

Table 3. Clinical Laboratory Parameters CC

Parameter	Flag Level*	Alert Level^	Conventional Units
Fasting Serum Triglycerides	≥400	≥600	mg/dL
	-	≥800	mg/dL
Platelet Count	< 100	< 75	10^9/L
Fasting Plasma Glucose	< 70	≤ 49	mg/dL
	≥140	> 270	mg/dL
Alanine aminotransferase	$\geq 2x ULN$	Pfizer std	IU/L
		flag for PCC	
	> 3x ULN	Pfizer std	IU/L
		flag for PCC	
	> 5x ULN	>8x ULN	IU/L

Parameter	Flag Level*	Alert Level^	Conventional Units
Aspartate aminotransferase	≥2x ULN	Pfizer std	IU/L
_		flag for PCC	
	> 3x ULN	Pfizer std	IU/L
		flag for PCC	
	> 5x ULN	>8x ULN	IU/L
Alkaline Phosphatase	$\geq 2x ULN$	Pfizer std	IU/L
		flag for PCC	
	> 3x ULN	Pfizer std	IU/L
		flag for PCC	
	> 5x ULN	Pfizer std	IU/L
		flag for PCC	
Gamma Glutamyl Transferase	> ULN	Pfizer std	IU/L
		flag for PCC	
Total Bilirubin	> 1.5x ULN	>3x ULN	mg/dL
Direct (Conjugated) Bilirubin	> ULN	Pfizer std	mg/dL
		flag for PCC	
Estimated glomerular filtration rate (eGFR)**	<60	Pfizer std	mL/min/1.73 m ²
		flag for PCC	
	<45	Pfizer std	mL/min/1.73 m ²
		flag for PCC	
	2.0	D0	T () (4 CO)

Table 3. Clinical Laboratory Parameters CCI

<30

Pfizer std

flag for PCC

mL/min/1.73 m²

PCC - Potential Clinical Concern

ULN - upper limit of normal as determined by the central laboratory

The safety events as defined in Table 3 will be summarized and the frequency of laboratory abnormalities (both number of occurrences and number of participants).

Across all the laboratory-related analytes (for safety and pharmacodynamics/biomarkers), inclusion of results when assessed at scheduled nominal visits must be (1) collected prior to AM dose of double-blinded study medication, and should be summarized as noted either for criteria (2) or criteria (3):

(2) Collection permitted to be nonfasted for the following analytes and will be permitted to be grouped with fasted results given that nonfasted state is not known to impact results

^{*}All flag level changes are cumulative from baseline (defined as result closest prior to dosing at Visit 5 (Day 1); reflect either threshold for entry criteria into study or clinically significant thresholds

[^]All alert changes are cumulative from baseline (defined as result closest prior to dosing at Visit 5 (Day 1); values when noted during the study, by central laboratory necessitates rapid notification (via fax/e-mail) to site and Study Clinician

^{**} eGFR should be based on cystatin-C - see Appendix 2.4 for derivations.

Table 4.	Laboratory	Assessments	(non-fasted)
----------	------------	-------------	--------------

Chemistry panel	Hematology	Other	Urinalysis
Total bilirubin	Hemoglobin	Cystatin-C (and eGFR	pH
Direct bilirubin	Hematocrit	using CKD-EPI-	Protein
Indirect bilirubin	RBC	Cystatin-C)	Glucose
Alk Phos	MCV	aPTT	Ketones
ALT	MCH	PT	Bilirubin
AST	MCHC	INR	Urobilinogen
GGT	WBC	Urine-drug-testing	Blood
Urea Nitrogen	Neutrophils (abs)	Serology testing	Nitrite
Creatinine	Lymphocytes (abs)	[HBsAg, HCVAb (and	Leukocyte esterase
Uric acid	Monocytes (abs)	if positive, reflex HCV	Microscopic UA
Calcium	Eosinophils (abs)	RNA), HIV]	
Total protein	Basophils (abs)	Alpha-1-antitrypsin	
Albumin	Platelets	Ceruloplasmin	
Creatine kinase	Reticulocyte count%	HbA1C	
Sodium	Reticulocyte count	hs-CRP	
Potassium		β-hCG	
Bicarbonate		FSH	
Chloride			

\mathbf{Or}

(3) The following analytes will only be included in summary outputs if collections are confirmed to be following an overnight fast of at least 8 hours (as recorded on the laboratory CRF page) as it is well known that fasting status impacts numerical results (or there is insufficient data regarding effect of meals on results).

Table 5. Laboratory Assessments (fasted)

Biomarkers	Lipid-related	Other Blood- related
% CDT	Total cholesterol	CCI
Plasma Glucose	HDL-C	
Plasma Insulin	Direct LDL-C	
Total Bile Acids	Triglycerides	
CK18-M30	Direct VLDL	
CK18-M65	Apolipoprotein A1	
ProC3	Apolipoprotein B total	
ProC6	Apolipoprotein B100	
Plasma PCSK9	Apolipoprotein B48	
Individual components of ELF Score (ie, HA, PIIINP, TIMP-	Apolipoprotein C3	
1)	Apolipoprotein E	
Adiponectin		
Individual components of HOMA-IR (i.e. Fasting Plasma	1	
Glucose and Fasting Plasma Insulin)	1	

, using these samples will be summarized in a stand alone report (outside of study-level CSR).

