6.6.2. Laboratory Data

Laboratory parameters will be summarized descriptively over time, and as described in Section 3.5.2. Individual plots of absolute values in Platelet Count, aPTT, INR vs time for participants with Platelet Count<100,000/mm3 after Day 1 to Week 48 will be produced as well as individual plots of absolute values in TG, FPG, FPI, ApoC3 vs time for participants with Fasting TG ≥ 400 mg/dL after Day 1 to Week 48.

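### The pre-dose condition in SAP 3.5.2 has no exception for Flag and Alert counts, so a valid scheduled safety result drawn after the morning dose is left out of them

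*SAP*

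**What the plan says.** SAP 3.5.2 lists the Table 3 parameters: triglycerides, platelets, fasting glucose, ALT, AST, ALP, GGT, total and direct bilirubin, and eGFR. For each it plans absolute values and changes by visit, plus the number of occurrences and of participants at Flag or Alert level. Below the table it repeats the plan: "The safety events as defined in Table 3 will be summarized and the frequency of laboratory abnormalities".

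An inclusion rule follows directly.

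- Its scope is stated as "Across all the laboratory-related analytes (for safety and pharmacodynamics/biomarkers"), so safety analytes are named.
- It governs "inclusion of results when assessed at scheduled nominal visits".
- Its first and mandatory condition is that the sample was "collected prior to AM dose of double-blinded study medication".
- The two further criteria concern fasting only. For Table 4 analytes the first of them reads "Collection permitted to be nonfasted for the following analytes", and these results may be pooled with fasted ones "given that nonfasted state is not known to impact results". Table 5 analytes must be fasted.

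SAP 6.6.2 points back to the same place: "Laboratory parameters will be summarized descriptively over time, and as described in Section 3.5.2".

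**The concern.** A by-visit mean benefits from samples taken under uniform conditions. A threshold count has a different purpose, which is to record whether a participant ever crossed a limit. The SAP applies one filter to both.

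For Table 4 analytes it explains why fasting does not matter. It does not say why having taken that morning's tablets should disqualify a platelet count or an ALT in someone who may have been dosed for weeks. Protocol 8.8 is more permissive even for biomarker samples: a scheduled post-dose collection is logged as a deviation, yet its result may still be judged evaluable.

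Platelet decline has its own stopping threshold (Protocol 8.2.8.2), and drug-induced liver injury is listed among the study risks (Protocol 2.3). Those are the parameters for which a complete count is wanted.

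**Working it through.** The plan gives no figure on this point to reproduce. The check is a reading of the text, followed by an illustration on assumed rates.

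**Does anything release Table 4 analytes from the pre-dose condition?**

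| Place | What it does | Releases them? |
|---|---|---|
| SAP 3.5.2, fasting criterion for Table 4 | Waives fasting | No |
| SAP 3.5.2, fasting criterion for Table 5 | Requires fasting | Not applicable |
| SAP 6.6.2 | Refers back to 3.5.2 | No |
| SAP 3.5.3 (liver-injury and Hy's law table, eDish plots) | Does not mention dose timing | Silent |
| SAP Appendix 2.1 | Windows planned and unplanned visits | No, but unplanned samples are outside the rule |

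Of the Table 3 parameters, platelets, ALT, AST, ALP, GGT, both bilirubins and eGFR are in Table 4. Triglycerides and plasma glucose are in Table 5. Neither document has an exception for the Flag and Alert counts. When every included result is counted, removing some can only lower the count or leave it unchanged.

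**Illustration of size.** Inputs:

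- 50 participants per arm (SAP 2.2).
- 10 scheduled on-treatment laboratory visits: Weeks 2, 4, 6, 8, 12, 16, 24, 32, 40 and 48 (SAP 3.5.2).
- *p*, the share of scheduled draws taken post-dose. It is not given, so 1%, 5% and 10% are assumptions, with draws treated as independent.

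Formulas:

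- Results left out per analyte per arm = 50 × 10 × *p*
- Chance that an abnormality seen at one scheduled visit only is lost = *p*; at two visits = *p*²
- Chance that at least one of three one-visit cases is lost = 1 − (1 − *p*)³

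| *p* | Results left out per arm | One-visit case lost | Two-visit case lost | At least one of three one-visit cases lost |
|---|---|---|---|---|
| 1% | 5 | 1% | 0.01% | 3.0% |
| 5% | 25 | 5% | 0.25% | 14.3% |
| 10% | 50 | 10% | 1% | 27.1% |

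One participant lost from a count in an arm of 50 is 1/50 = 2 percentage points. That needs every qualifying result for the participant to have been a scheduled, post-dose draw. The step is smaller in the 75 mg and 150 mg BID groups if former QD participants take them above 50.

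**The case against.** The case for leaving the rule alone has real weight.

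- **Post-dose draws should be uncommon.** Protocol 5.4.2 tells participants to arrive undosed and to take study medication after the pre-dose procedures. This stands.
- **Repeat samples are not caught.** The rule names scheduled visits only, and Appendix 2.1 windows unplanned data. Platelets below the lower limit of normal call for an unplanned visit (Protocol 8.2.8.2). Transaminases above 3 × ULN call for more frequent monitoring, and potential Hy's law cases for prompt re-evaluation (Protocol Appendix 6). This stands, with one limit: if the repeat has recovered, the excluded value was the only one showing the abnormality.
- **Other routes report the same events.** Clinically relevant changes are recorded as adverse events (Protocol 8.2.5). Potential Hy's law cases confirmed on repeat testing, with no other cause found, are SAEs. Drug-induced liver injury is adjudicated (Protocol 9.6) and summarized (SAP 6.3.7). Alert values go rapidly to the site and the study clinician. This largely stands. The adverse event route is weaker for ALT and AST, because abnormalities tied to the underlying disease are not adverse events unless judged more severe than expected (Protocol Appendix 3).
- **The rule is arm-neutral.** It is pre-specified and applied in a double-blind trial, and nothing in the documents points to different rates of post-dose draws between arms.

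A reader might infer three stronger things that the documents do not support:

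1. That safety signals disappear from the trial. The routes above rule this out.
2. That the Hy's law table and eDish plots are certainly filtered. They sit in SAP 3.5.3, which does not state the condition, so carrying it across is inference.
3. That a post-dose safety draw is a protocol deviation. The protocol says this for PK samples (8.5) and biomarker samples (8.8); no equivalent statement was found for routine safety laboratory samples.

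**Conclusion.** The point holds in a limited form. As written, SAP 3.5.2 leaves valid scheduled post-dose results for Table 4 safety analytes out of the Flag and Alert counts, without a reason and without an exception. The loss falls mainly on abnormalities seen at one scheduled visit and not repeated. It concerns the completeness of descriptive laboratory counts. Participant monitoring is not affected, and no bias between arms is shown.

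The size cannot be derived from the documents. The 1% to 10% range is an assumption, and the low end is more plausible given the instruction to arrive undosed. The change is still worth making before unblinding: it costs almost nothing, and the filter has no stated benefit for these counts.

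**What to change.** In SAP 3.5.2, separate threshold counts from by-visit summaries:

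- Keep the pre-dose condition for Table 5 analytes, and leave their fasting rule untouched. Triglyceride and glucose counts therefore remain filtered.
- Keep the pre-dose condition for by-visit summaries of all analytes, if uniform sampling conditions are wanted there.
- For Table 4 analytes, base the Table 3 Flag and Alert counts on all post-baseline results, scheduled or unplanned, regardless of dose timing.

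In SAP 3.5.3, state that the liver-injury and Hy's law table and the eDish plots use the same unfiltered data.

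The cost is a sentence or two in each section and a second inclusion flag in the laboratory dataset. No new data are needed.
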